8. STUDY PROCEDURES

The procedures required for subject evaluation at each study visit are presented in the Schedule of Assessments, [REDACTED]. The timing of each study day is relative to the day of initial dosing (Day 1). Visit windows are provided where allowed to allow flexibility in maintaining the study visit schedule for participating subjects.

8.1. Study Visits

8.1.1. Screening

The screening period may take up to 30 days to provide flexibility in scheduling and adequate washout time for subjects taking certain medications. Questions on subject eligibility will be referred to the Sponsor or their designee. Individuals who do not meet the criteria for participation in this trial (screen failure) may be rescreened once, if deemed acceptable by the Investigator and Sponsor. Rescreened subjects will be re-consented and assigned a new subject number.

8.1.2. Day 1 through Study Exit

Subjects will complete all procedures as summarized in the Schedules of Assessments, [REDACTED] and detailed below on Day 1 through their Study Exit.

8.1.3. Unscheduled Visits

Additional visits may be scheduled, as necessary, and any safety procedures may be conducted at the discretion of the Investigator. All data collected will be recorded in the eCRF and laboratory database, as appropriate.

8.2. Study Procedures

8.2.1. Demographics/Medical History

Demographic information including age, gender, race, and ethnicity will be collected for each subject.

A complete medical history will be collected as part of Screening and should include all clinically relevant past or coexisting medical conditions or surgeries. History of CIndU, date of diagnosis, and any prior or current medications for CIndU will be recorded in the eCRF accordingly. Such history will be supported by medical records, as available.

The medical history will be updated prior to treatment, should new findings be present after the Screening visit.

8.2.2. Vitals Signs

Vital signs, including body temperature, respiratory rate (breath per minute), pulse (beats per minute), and blood pressure (mmHg), will be obtained with the subject in the seated position, after sitting for at least 5 minutes. Any abnormal findings which are new or worsened in severity and clinically significant, in the opinion of the Investigator, will be recorded as an AE.

When vital signs measurements coincide with a blood draw, they should be performed before the blood collection.

8.2.3. Height and Weight

Height will only be collected at Screening. Weight will be collected at all other timepoints as indicated in [REDACTED]

8.2.4. Physical Exam

A complete physical examination will be conducted at study visits as detailed in the Schedule of Assessments, [REDACTED]

The complete physical examination will cover general appearance, dermatological, head, ears, eyes, nose, throat, respiratory, cardiovascular, abdominal, neurological, musculoskeletal, and lymphatic body systems.

8.2.5. 12-Lead ECG

A 12-lead ECG will be conducted at study visits as detailed in the Schedule of Assessments, [REDACTED] Prior to measurement, subjects will be required to have rested for at least 10 minutes in a supine position. Study sites will use 12-lead ECG machines capable of recording ventricular rate, the PR, QRS, QT, QTcF, and RR intervals. The Sponsor or designee will help procure equipment for sites that do not have access to a 12-lead ECG. When ECGs coincide with a blood draw, they should be performed before the blood collection.

8.2.6. Laboratory Assessments

Laboratory tests will be collected as stipulated in the Schedule of Assessments, [REDACTED] will be analyzed at a central laboratory. Day 1 samples will be collected prior to study drug administration. Laboratory assessments may be repeated once during screening to qualify a subject for the study. All laboratory assessments, for screening and during the trial conduct, must be collected using the central laboratory. Sample handling, processing, and shipping information will be detailed in the Laboratory Manual.

8.2.6.1. Hematology, Blood Chemistry, and Urinalysis

Hematology, blood chemistry, and urinalysis samples will be collected to evaluate safety. Analytes to be tested are summarized in [REDACTED]

Table 3: Laboratory Analytes for Safety Evaluation

Hematology	Blood Chemistry	Urinalysis

 Hematocrit Hemoglobin Red blood cell (RBC) count White blood cell count and differential (%) Mean corpuscular hemoglobin (MCH) 	
 Sodium Potassium Magnesium Chloride Calcium, phosphorus CO₂ Uric acid 	
 pH Specific gravity Protein Glucose Ketones Bilirubin Blood

Hematology	Blood Chemistry	Urinalysis

 • Mean corpuscular hemoglobin concentration (MCHC) • Mean corpuscular volume • RBC morphology • Platelet count • Absolute neutrophils • Absolute lymphocytes • Absolute monocytes • Absolute eosinophils • Absolute basophils 	
 • Blood urea nitrogen (BUN) • Creatinine • Total protein • Albumin • Aspartate aminotransferase (AST) • Alanine aminotransferase (ALT) • Alkaline phosphatase • Bilirubin (total, indirect, and direct) • Cystatin C • [REDACTED] • [REDACTED] 	
 • Nitrite • Urobilinogen • Leukocyte esterase • Qualitative assessment of color and clarity • Microscopic analysis (as required)

8.2.6.2. Pregnancy Testing

Pregnancy testing will be performed for WOCBP. Serum pregnancy testing will be conducted at Screening, Week 4, and Week 6/Study Exit/Early Withdrawal. On Day 1 and unscheduled visits, pregnancy testing will be urine.

If a urine pregnancy test is positive prior to dosing, a serum pregnancy test may be drawn at the discretion of the Investigator to confirm the pregnancy. A negative urine or serum pregnancy test must be demonstrated to confirm subject eligibility prior to dosing.

A blood sample to test serum FSH will be collected from female subjects who are under 55 and post-menopausal (defined by 12 months of amenorrhea in the absence of other biological causes) at Screening.

8.2.6.3. Pharmacokinetic Sampling

A blood sample will be collected per the Schedule of Assessments, [REDACTED] at any time during the specified visit. Sample handling, processing, and shipping information will be detailed in the Laboratory Manual.

[REDACTED] [REDACTED]

[REDACTED]
[REDACTED]
[REDACTED]

8.2.6.5. Immunoglobulin E (IgE)

As part of the blood chemistry panel at Screening, pre-treatment IgE levels will be evaluated as a baseline characteristic for all subjects. The Sponsor will review screening IgE levels for all subjects [REDACTED]

[REDACTED]
[REDACTED]
[REDACTED]
[REDACTED]

8.2.7. Standardized Provocation Tests

Depending on the CIndU subtype, subjects will undergo provocation testing at the visits outlined in the Schedule of Assessments, [REDACTED] Details on how to perform the provocation tests will be outlined in the Provocation Test Manual. Each provocation test will be evaluated approximately 10 minutes after completion of provocation. The start and end time of the provocation test and the beginning of the provocation test evaluation will be recorded in the eCRF.

Provocation tests should be performed by the same administrator and evaluator, on the same arm for the duration of participation, whenever possible.

8.2.7.1. Cold Urticaria - TempTest

The TempTest is an instrument used to elicit symptoms of cold and heat urticaria. The instrument is a small device containing a single 2 mm wide 350 mm long U-shaped Peltier element generating a temperature gradient from 4° to 44 °C along its length. The subject will place the volar aspect of their forearm on the temperature gradient side of the device for approximately 5 minutes.

[figure not shown]
A positive response to the provocation test is defined as a palpable wheal at the test site. Approximately 10 minutes after completion of provocation (i.e., approximately 15 minutes from the start of the test), the resultant wheal will be outlined on the TempTest provided stencil. The critical threshold temperature (CTT), defined as the highest temperature that elicits a wheal response, will be determined and recorded. The stencil with wheal markings will be filed in the subject's source documents.

8.2.7.2. Symptomatic Dermographism - FricTest

The FricTest is an instrument used to diagnose symptomatic dermographism ([Mlynek 2013](#)). The FricTest is a flat plastic comb (85 x 55 mm) with four round-ended plastic pins 3 mm in diameter, with lengths of 3.0, 3.5, 4.0, and 4.5 mm, respectively. For provocation, the comb is held perpendicular to the volar forearm and constant, sufficient pressure is applied so that all pins make contact with the skin and are almost, but not completely, invisible. The instrument is then stroked across the skin across approximately 60 mm. After about 10 minutes, the resultant wheals are evaluated. A clearly visible and palpable linear wheal with a width of ≥ 3 mm (the diameter of the pins) is considered a positive response. The total number of linear wheals with a width of ≥ 3 mm is the Total Fric Score (TFS).

8.2.8. Pruritus-Numerical Rating Scale (NRS)

Prior to and approximately 10 minutes after completion of the provocation test (i.e., immediately after the wheal evaluation), the subject will be asked to rate the severity of their pruritus at the site of the provocation test [REDACTED]

9. TREATMENT OF SUBJECTS

9.1. Description of Study Drug

[REDACTED]

9.2. Concomitant Medications

All medications (including over the counter [OTC] agents) taken by subjects after Screening until the last study day will be documented as concomitant medications in the eCRF.

The following medications are prohibited for the timeframe specified prior to the Day 1 visit and while on study:

- Biologics (e.g., omalizumab, dupilumab, tezepelumab, ligelizumab) 120 days or 5 half-lives (whichever is longer) prior to Day 1,
- Cyclosporine, methotrexate, sulfonamides, systemic glucocorticoids (e.g., prednisone), or mycophenolate mofetil 28 days prior to Day 1,
- A live or live-attenuated vaccine for 14 days prior to Day 1,
- Leukotriene inhibitors (e.g., montelukast, zafirlukast) 14 days prior to Day 1 (if being used to treat CIndU or CSU),
- H2-receptor antagonists [e.g., ranitidine, famotidine]) 14 days prior to Day 1 (if being used to treat CIndU or CSU),
- Long-acting antihistamines (e.g. H1-receptor antagonists such as, loratadine, desloratadine, fexofenadine, cetirizine, and levocetirizine) 7 days prior the first provocation test during the screening period,
- Short-acting antihistamines (e.g., H1-receptor antagonists such as hydroxyzine, diphenhydramine) for 3 days prior to the first provocation test during the screening period.

10. STUDY DRUG MATERIALS AND MANAGEMENT

10.1. Study Drug

[REDACTED]

[REDACTED]

[REDACTED]

[REDACTED]

[REDACTED]

[REDACTED]

[REDACTED]

[REDACTED]

[REDACTED]

[REDACTED]

[REDACTED]

[REDACTED]

[REDACTED]

10.4. Study Drug Dispensation, Administration, and Return

Subjects will be dispensed study drug on Day 1, Week 1, Week 2, and Week 3 to support at-home dosing between clinic visits. Subjects will be administered their first dose of study drug at the study center.

For QD doses, subjects will be instructed to orally self-administer study drug with approximately 240 mL of water at approximately the same time every morning starting on Day 2 through Week 4.

For BID doses, subjects will be instructed to orally self-administer study drug with approximately 240 mL of water every morning and evening, approximately 12 hours apart. On study visit days, subjects will take study drug at the study center, as feasible. The investigator and study personnel should promote compliance by instructing the subject to take the study drug exactly as prescribed and by stating that compliance is necessary for the subject's safety and validity of the study. The subject will be instructed to contact the site if he/she is unable to take the study drug as prescribed for any reason. Compliance with study drug dosing will be reviewed at each visit and all remaining study drug must be returned to the site at each visit for study drug accountability. Adherence to treatment will be assessed by direct questioning and by maintaining adequate study product dispensing and return records. Subjects will be provided a paper diary to record any missing doses and to record the timing of the last administration of study drug prior to the Week 1, 2, and 4 provocation tests. Missing doses and the time of administration prior to the provocation tests at Week 1, 2, and 4 will be recorded in the eCRF.

10.5. Study Drug Accountability and Disposal

The Investigator or designee will be responsible for documenting drug accountability at the study center. Study drug accountability records will document the receipt, dispensing, and return of study drug and provide a complete account of all used and unused drug product.

Study drug accountability records will be reviewed by the Sponsor or designee. Following final accountability, instructions will be provided to the site regarding study drug return and destruction.

11. SAFETY MONITORING

11.1. Safety Parameters

Subjects will be monitored throughout the study by the clinical staff for AEs.

Safety parameters, including vital signs, physical exam results, laboratory results, and the 12-lead ECG, will be assessed by the Investigator or designee.

Subjects will be advised to notify their healthcare professional(s) that they are participating in a clinical research study on a drug called EVO756 before taking any medicines or undergoing any medical procedures.

11.2. Adverse and Serious Adverse Events

11.2.1. Definition of Adverse Events

11.2.1.1. Adverse Event (AE)

An AE is the development of an undesirable medical condition or the deterioration of a pre-existing medical condition following or during exposure to a pharmaceutical product, whether or not considered causally related to the product. In clinical studies, an AE can include an undesirable medical condition occurring at any time, including baseline or washout periods, even if no study treatment has been administered.

Abnormal laboratory, vital signs, physical exam, and ECG findings may be assessed as AEs only if they are found to be clinically significant by the investigator, correlate with a clinically relevant presentation, and/or require intervention.

11.2.1.2. Serious Adverse Event (SAE)

An AE or suspected AE reaction is considered serious if, in the view of either the Investigator or Sponsor, it results in any of the following outcomes:

- Death;
- Life-threatening;

An AE or suspected AE is considered “life threatening” if, in view of either the Investigator or Sponsor, its occurrence places the study subject at immediate risk of death. It does not include an event that, had it occurred in a more severe form, might have caused death.

- Requires in-patient hospitalization or prolongation of existing hospitalization.

Any hospital admission will be considered an in-patient hospitalization, regardless of duration. An emergency room visit without hospital admission will not be recorded as an SAE under this criterion, nor will hospitalization for a procedure scheduled before signing of informed consent. However, unexpected complications and/or prolongation of hospitalization that occur during elective surgery should be recorded as AEs and assessed for seriousness. Admission to the hospital for a pre-planned procedure or social or

situational reasons (e.g., no place to stay, lives too far away to come for hospital visits) will not be considered in-patient hospitalizations.

- Persistent or significant disability or incapacity.
- Congenital abnormality or birth defect.
- It is an important medical event that may jeopardize the subject or may require medical intervention to prevent one of the outcomes listed above.

Important medical events that may not result in death, be life-threatening, or require hospitalization may be considered an SAE when, based upon appropriate medical judgment, they may jeopardize the study subject and may require medical or surgical intervention to prevent one of the outcomes listed above. Examples of such medical events include allergic bronchospasm requiring intensive treatment in an emergency room or at home, blood dyscrasias or convulsions that do not result in in-patient hospitalizations, or the development of drug dependency.

11.2.2. Reporting of Adverse Events

AEs spontaneously reported by the subject and/or in response to an open question from the study personnel or revealed by observation will be recorded during the study at the study center.

AEs should be recorded on the eCRF from the time the subject has signed informed consent through the last study visit. Any changes in the subject's status between signing informed consent, up to the time administration of the first dose of study drug will be recorded as a pre-treatment AE. Any AE occurring after administration of the first dose of study drug will be considered a treatment emergent AE (TEAE).

The AE term should be reported in standard medical terminology when possible.

Any subject who has an AE (whether serious or non-serious) or clinically significant test value will be evaluated by the Investigator or designee and will be treated and/or followed up until the symptoms or values return to normal or to clinically acceptable levels, or stabilize, as judged by the Investigator.

Unless a diagnosis is available, signs and symptoms must be reported as individual AEs in the eCRF; a diagnosis is preferred.

For each AE, the investigator will evaluate and report the onset date, resolution or stabilization date, intensity, causality, action taken, serious outcome (if applicable), and whether or not it caused the subject to discontinue the study.

Intensity will be assessed according to the National Cancer Institute (NCI) Common Terminology Criteria for Adverse Events (CTCAE), Version 5.0, 2017. The NCI Common Terminology Criteria for Adverse Events is a descriptive terminology which can be utilized for AE reporting. A grading (severity) scale is provided for each AE term. Grade refers to the severity of the AE. The CTCAE displays Grades 1 through 5 with unique clinical descriptions of severity for each AE based on this general guideline:

- Grade 1 – Mild; asymptomatic or mild symptoms; clinical or diagnostic observations only; intervention not indicated.
- Grade 2 – Moderate; minimal, local or noninvasive intervention indicated; limiting age-appropriate instrumental activities of daily living (ADL).

- Grade 3 – Severe or medically significant but not immediately life-threatening; hospitalization or prolongation of hospitalization indicated; disabling; limiting self-care ADL.
- Grade 4 – Life-threatening consequences; urgent intervention indicated.
- Grade 5 – Death related to AE.

It is important to distinguish between serious and severe AEs. Severity is a measure of intensity whereas seriousness is defined by the criteria under Section 11.2.1.2. An AE of severe intensity may not be considered serious (e.g., ‘severe’ headache). Reporting of Serious Adverse Events

SAEs must be reported to the Sponsor or designee within 24 hours of awareness of the event from the time the subject has signed informed consent through the last study visit or until resolution, whichever is sooner, using SAE form. In particular, if the SAE is fatal or life-threatening, notification to the Sponsor or designee, must be made immediately, irrespective of the extent of information available.

Reporting should be done by sending the completed SAE form to the following email address (faxing can also be done as a second option in case emailing is not possible).

[REDACTED]
[REDACTED]
[REDACTED]

In all cases, the Investigator should continue to monitor the clinical situation and report all material facts relating to the progression or outcome of the SAE. The Investigator may be required to provide supplementary information as requested by the Sponsor or its designee.

When reporting SAEs, the following additional points should be considered:

- When the diagnosis of an SAE is known or suspected, the Investigator should report the diagnosis or syndrome as the primary SAE term, rather than as signs or symptoms; signs, symptoms and tests that support the diagnosis should be provided.
- Death should not be reported as an SAE, but as an outcome of a specific SAE, unless the event preceding the death is unknown. If an autopsy was performed, the autopsy report should be provided.

The Sponsor or designee will process and evaluate all SAEs as soon as the reports are received. For each SAE received, the Sponsor will decide as to whether the criteria for expedited reporting to relevant regulatory authorities have been met.

The Sponsor will assess the expectedness of each SAE to the study treatment.

11.2.3. Relationship to Study Drug

An Investigator who is qualified in medicine must make the determination of relationship to the investigational product for each AE (not related, related). The Investigator should decide whether, in his or her medical judgment, there is a reasonable possibility that the event may have been caused by the investigational product.

The relationship of the AE to the study treatment will be based on the following two definitions:

Not related: An AE is defined as “not related” if the AE is not judged to have a reasonable possibility to be associated with the study drug and/or is attributable to another cause.

Related: An AE is defined as “related” where a causal relationship between the event and the study drug is reasonably likely. A reasonable causal relationship is meant to convey that there are facts (e.g., evidence such as dechallenge/ rechallenge) or other clinical arguments to suggest a causal relationship between the AE and study treatment, the AE follows a reasonable temporal sequence from study drug administration and cannot be reasonably explained by the known characteristics of the subject’s clinical state.

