### 14.1 Adverse Events

AEs will be coded according to the MedDRA, version 27.0.

Treatment emergent adverse events (TEAEs) are defined as any AEs with onset date, and time (if available), on or after the date, and time (if applicable) of the first dose of study drug. [REDACTED]

[REDACTED] In the case where it is not possible to define an AE as treatment emergent or not, the AE will be classified as treatment emergent.

An overall summary table for AEs will be provided. The number of events and the number and percentage of subjects who experienced at least one AE, TEAE, TEAE by greatest reported relationship to study drug, TEAE by worst reported severity, TEAE with an outcome of death, serious TEAE, non-serious TEAE, TEAE leading to discontinuation from study drug, and TEAE leading to discontinuation from study will be presented.

Incidence of TEAEs will be summarized by SOC and PT. Subjects experiencing multiple TEAEs within a SOC will be counted only once for that SOC. Similarly, subjects experiencing multiple TEAEs within a PT will be counted only once for that PT. TEAEs will be sorted alphabetically by SOC and within each SOC, PTs will be presented by decreasing order of total frequency.

Incidence of TEAEs will be further broken down by greatest reported relationship with study drug, where a treatment-related TEAE is defined as any TEAE that is assessed by the investigator as related to study drug while not treatment-related TEAE is defined as any TEAE that is assessed as not related to study drug. Subjects experiencing multiple TEAEs within the same SOC/PT but in different categories of relationship to study drug will be reported only once under the greatest reported relationship to study drug. A TEAE with an unknown relationship will be considered as treatment-related.

Incidence of TEAEs will also be further broken down by worst reported severity. A severe adverse event is defined as any AE with a toxicity grade of 3 or higher. Subjects experiencing multiple TEAEs within the same SOC/PT but in different categories of severity will be reported only once under the worst severity. A TEAE with an unknown severity will be considered as severe.

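### Protocol 11.2.3 applies three causality tests that do not agree, so an AE with a reasonable possibility of drug causation can be coded not related or fit neither code

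*Protocol*

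**What the plan says.** Protocol 11.2.3 uses a two-level scale, related or not related, and contains three statements of the test.

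- **Opening question.** The investigator decides whether "there is a reasonable possibility that the event may have been caused by the investigational product".
- **Not related.** The AE "is not judged to have a reasonable possibility to be associated with the study drug and/or is attributable to another cause".
- **Related.** This applies "where a causal relationship between the event and the study drug is reasonably likely". The text goes on to require supporting facts or clinical arguments, a reasonable temporal sequence, and that the event "cannot be reasonably explained by the known characteristics of the" subject's clinical state.

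Between the opening question and the definitions, the section states: "The relationship of the AE to the study treatment will be based on the following two definitions". On a plain reading the definitions govern the code, not the opening question.

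SAP 14.1 carries the code straight into the tables: "a treatment-related TEAE is defined as any TEAE that is assessed by the investigator as related to study drug". An unknown relationship is counted as treatment-related. There is no other safeguard on the code.

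**The concern.** Two categories on a binary scale should be complements, and both should turn on the question that the investigator was asked. Here the bar for related is higher than the opening question, and the bar for not related can be met by a route that the opening question does not contain. An investigator who sees a reasonable possibility of drug causation can therefore follow the text and still arrive at not related, or find that neither definition fits.

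This matters more here than in a controlled trial. Safety and tolerability are the primary objective (Protocol 5.1). The study is open label, and both treatment groups receive EVO756 (SAP 3.3), so there is no untreated comparator against which to judge the background rate of an event. There is no data monitoring committee (SAP 4.1). Investigator attribution therefore carries much of the weight in any statement about drug-related events. Data from all sites are pooled (SAP 7.2), so if some sites work from the opening question and others from the definitions, the related-TEAE table mixes two standards.

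**Working it through.** The documents give no figure on this point, so there is none to reproduce. The check is logical. For each AE, let:

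- P = there is a reasonable possibility of drug causation
- L = causation is reasonably likely, with supporting facts and a reasonable temporal sequence (L implies P)
- A = the AE is attributed to another cause
- E = the AE is reasonably explained by the subject's clinical state

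The three tests in 11.2.3 are then:

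- Opening question: related if P
- Not-related definition: (not P) or A
- Related definition: L and not E

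Four yes/no items give 16 combinations. The 4 with L but not P are impossible, which leaves 12. In the 4 with P false, every test gives not related. The 8 with P true, for which the opening question always says related, are:

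| L | A | E | Result under the two definitions |
|---|---|---|---|
| no | no | no | neither |
| no | no | yes | neither |
| no | yes | no | not related |
| no | yes | yes | not related |
| yes | no | no | related |
| yes | no | yes | neither |
| yes | yes | no | both |
| yes | yes | yes | not related |

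Totals: 1 related only, 3 not related only, 1 both, 3 neither (1 + 3 + 1 + 3 = 8). These count logical cases, not event frequencies. They show direction: no combination turns a not-related answer to the opening question into a related code.

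Two more generous readings show how far the result depends on interpretation.

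- *Attribution to another cause means that no reasonable possibility remains* (A excludes P). The rows with A drop out and 4 remain: 1 related, 3 neither.
- *An explanation by clinical state always counts as attribution to another cause* (E implies A). The two rows with E but not A drop out and 6 remain: 1 related, 3 not related, 1 both, 1 neither.

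With both readings applied, two rows remain: likely (related) and possible but not likely (neither). So the gap between a reasonable possibility and reasonably likely survives even the kindest reading.

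For scale only: SAP Appendix 1 bases these percentages on all subjects in the population. If all of the approximately 30 planned subjects are treated, each subject whose only related TEAE is recoded moves the overall related-TEAE incidence by 1/30 = 3.3 percentage points. The step is larger within a treatment group, because the denominator is smaller.

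**The case against.** The strongest defence is that 11.2.3 speaks of an AE that is attributable to another cause. That is a positive finding by a medically qualified investigator, not the mere existence of an alternative. Someone who has made that finding has, in ordinary practice, largely answered the opening question too. This stands as an argument against reading the text as compulsion. A reader might infer that any conceivable alternative cause forces a not-related code; the wording does not say so. The defence does not close the gap, because an event can be attributed mainly to another cause while a drug contribution remains reasonably possible, and the either-or wording then permits not related.

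A reader might also infer that worsening urticaria or pruritus can never be coded related, because every subject has CIndU. The documents do not support that. The clause concerns known characteristics of the individual subject, and a new or different presentation may fall outside them. The clause also sits only in the related definition. Failing it does not by itself meet the not-related definition, so the code is indeterminate, not forced.

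On impact, several safeguards stand. SAP 14.1 summarises all TEAEs, serious TEAEs and TEAEs leading to discontinuation regardless of causality, and lists every AE with its verbatim term, onset and relationship, so re-review is possible. All SAEs go to the sponsor within 24 hours with no causality filter, and "the Sponsor will decide as to whether the criteria for expedited reporting to relevant regulatory authorities have been met" (Protocol 11.2.2). A reader might infer that SAEs would be missed; they would not. The SAP default to treatment-related helps only when the relationship is unknown. Since 11.2.3 requires one of two codes, an event that fits neither definition will usually still be given one.

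**Conclusion.** The inconsistency is on the face of Protocol 11.2.3 and should be corrected. The three tests are not equivalent. An AE with a reasonable possibility of drug causation can be coded not related, or can be left without a determinate code, and sites may differ on the same event.

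The consequence is a possible under-count of related TEAEs in the SAP 14.1 tables. Under-counting is the likely direction, not a demonstrated result. Its size cannot be derived, because nothing in the documents says how many events would have both a possible drug cause and a competing explanation. A specific percentage fall in the related count would be an assumption restated as a conclusion. Only the related/not-related split is affected.

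The conclusion rests on two readings: that the two definitions govern the code, as the section states, and that reasonably likely is a higher bar than a reasonable possibility. If every investigator worked from the opening question alone, the problem would not arise in practice, but the text does not ensure that.

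**What to change.** Make the protocol's own opening question the single test, with complementary categories:

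- *Related:* there is a reasonable possibility that study drug caused the event, even if another cause may have contributed.
- *Not related:* there is no reasonable possibility that study drug caused the event.

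Delete the limb on attribution to another cause from the not-related definition, and replace the reasonably-likely threshold in the related definition. Keep temporal sequence, dechallenge or rechallenge, alternative causes and the subject's clinical state as factors that the investigator weighs, not as automatic exclusions. Protocol 12.3 uses graded terms for relatedness that the two-level scale does not contain; the two sections must be reconciled to one scale.

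The cost is a few sentences in 11.2.3, put through a protocol amendment with IRB approval (Protocol 16.4), and a reminder to sites. SAP 14.1 needs no change. AEs already coded under the present text would need a second look by the investigators, or the related counts would mix two standards. The reported related-TEAE rate may rise somewhat.
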